Table 2Schedule of activities for participants who have discontinued treatment with durvalumab /placebo

	Time since last dose of IP								
	Day (±3)	±3) Months (±1 week)						12 months	
Evaluation	30	2	3	4	6	8	10	then every 2 months (±2 weeks) ^a	For details, see Section
CCI									8.5
Tumour assessment (CT or MRI) (RECIST 1.1) ^j	On-study tumour assessments occur $q8w \pm 1$ week for the first 48 weeks (relative to the date of randomisation) and then $q12w \pm 1$ week thereafter until RECIST 1.1-defined radiological progression plus 1 or more additional follow-up scans for confirmation of progression until confirmed radiological progression, the end of study, death, study discontinuation, or Sponsor decision (whichever comes first). The on-study schedule of $q8w \pm 1$ week (relative to the date of randomisation) for the first 48 weeks and then $q12w \pm 1$ week thereafter MUST be followed regardless of any delays in dosing. Additional scans to be completed per standard practice post-progression.							8.1	

Participants on Survival Follow-up at the time of final DCO for the study will be considered to have completed the study and will continue to receive treatment per local standard of care.

- ^b Will be administered using a site-based electronic device. It is preferred that PRO questionnaires are completed prior to any other study procedures and before discussion of disease progression to avoid biasing the participant's responses to the questions.
- ^c For women of childbearing potential only. A urine or serum pregnancy test is acceptable.
- ^d WHO/ECOG performance status should also be collected at other study site visits that the participant attends, if appropriate study site staff are available to collect such information. In addition, WHO/ECOG performance status should be provided when information on subsequent anticancer therapy is provided, where possible.
- e Details of any treatment for NSCLC (including surgery) after the last dose of IP must be recorded in the eCRF. At minimum, collect the start date and description of the subsequent anticancer therapy.

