- ^d Bicarbonate (where available), chloride, creatinine clearance, gamma glutamyltransferase, and magnesium testing are to be performed at Baseline, on Day 1 (unless all part II screening laboratory clinical chemistry assessments are performed within 3 days prior to Day 1), and if clinically indicated.
- ^e If TSH is measured within 14 days prior to Day 1 (first infusion day), it does not need to be repeated at Day 1.
- ^f Free T3 or free T4 will only be measured if TSH is abnormal or if there is a clinical suspicion of an AE related to the endocrine system.
- AE Adverse event; ALT Alanine aminotransferase; AST Aspartate aminotransferase; T₃ Triiodothyronine;

T₄ Thyroxine; TSH Thyroid-stimulating hormone; WT Body weight.

Absolute neutrophil count ^a	Absolute lymphocyte count ^a
Haemoglobin	Platelet count
Total white blood cell count	
^a Should be recorded as absolute counts other than percentages.	

Table 9Coagulation Parameters

Activated partial thromboplastin time ^a	International normalised ratio ^a

^a Can be recorded as absolute counts or as percentages. Total white blood cell count therefore has to be provided.

Note: For coagulation parameters, activated partial thromboplastin time and international normalised ratio are to be assessed at part II screening and as clinically indicated.

Table 10Urinalysis

Bilirubin	Ketones
Blood	pH
Colour and appearance	Protein
Glucose	Specific gravity

Note: Urinalysis should be done at Baseline (part II screening), and then as clinically indicated. Note: Microscopy should be used as appropriate to investigate white blood cells and use the high power field for red and white blood cells.

If a participant shows an AST or ALT $\ge 3 \times$ ULN together with total bilirubin $\ge 2 \times$ ULN, refer to Appendix D for further instructions on cases of increases in liver biochemistry and evaluation of Hy's Law. These cases should be reported as SAEs if, after evaluation, they

meet the criteria for a Hy's Law case or if any of the individual liver test parameters fulfil any of the SAE criteria.

All participants should have further chemistry profiles performed at 30 days (\pm 3 days), 2 months (\pm 1 week), and 3 months (\pm 1 week) after permanent discontinuation of IP (see the SoAs).

Any clinically significant abnormal laboratory values should be repeated as clinically indicated and recorded on the eCRF. Situations in which laboratory safety results should be reported as AEs are described in Section 8.3.7.

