4.1 General principles

Efficacy and PRO data will be summarised and analysed on the mITT set. PK data will be summarised on the PK analysis set. Safety and treatment exposure will be summarised based upon the safety analysis set, except deaths that will be analysed on the ITT set.

Immunogenicity data will be summarised on the ADA analysis set. Study population and demography data will be summarised based upon the mITT set.

Selected analyses based on the mITT set will be repeated on the ITT set. For supporting listings, those will be produced on ITT and mITT patients will be identified.”

All data collected will be presented in data listings by treatment group and subject number. All summaries will be presented by treatment group, unless otherwise specified.

A year is defined to be 365.25 days and a month is defined to be 30.4375 days.

The below mentioned general principles will be followed throughout the study:

- Descriptive statistics will be used for all variables, as appropriate, and will be presented by treatment arm. Continuous variables will be summarised by the number of observations, mean, standard deviation, median, upper and lower quartiles, minimum, and maximum. For log transformed data it is more appropriate to present geometric mean, coefficient of variation (CV), median, minimum and maximum. Categorical variables will be summarised by frequency counts and percentages for each category.
- Unless otherwise stated, percentages will be calculated out of the population total and for each treatment arm.
- For continuous data, the mean and median will be rounded to 1 additional decimal place compared to the original data and rounded up (i.e., if original data is provided to 1 decimal place, a mean of 2.425 will become 2.43). The standard deviation will be rounded to 2 additional decimal places compared to the original data. Minimum and maximum will be displayed with the same accuracy as the original data.
- For categorical data, percentages will be rounded to 1 decimal place.
- Results of all statistical analysis will be presented using a 95% CI and 2-sided p-value, unless otherwise stated.
- P-values will be rounded to 3 decimal places. P-values less than 0.0005 (e.g. 0.0002) will not be rounded to 3 decimal places (e.g. 0.000) but instead be displayed as <0.001. P-values output as <0.0001 by statistical software will not be rounded and displayed in the same way ('<0.0001').
- SAS® Enterprise Guide (EG) will be used for all analyses.

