4.2.5.2 Laboratory assessments

Data obtained up until the 90 days following discontinuation of study treatment (durvalumab/placebo) or until the initiation of the first subsequent anti-cancer therapy (excluding palliative radiotherapy) following discontinuation of study treatment (whichever occurs first) will be used for reporting. This will more accurately depict laboratory toxicities attributable to study treatment only as some toxicities up to 90 days following discontinuation of the study treatment are likely to be attributable to subsequent therapy.

However, to assess the longer term toxicity profile, some summaries of laboratory data will be produced containing data collected up until 90 days following discontinuation of the study treatment (i.e., without taking subsequent therapy into account).

Any data post 90 days after the last dose of the study treatment will not be summarised.

Data summaries will be provided in preferred units.

Scatter plots (shift plots) of baseline to maximum value/minimum value (as appropriate) on-treatment may be produced for certain parameters if warranted after data review.

For continuous laboratory assessments, absolute value and change from baseline will be summarised using descriptive statistics at each scheduled assessment time by actual treatment group.

Shift tables for laboratory values by worst CTCAE grade will be produced, and for specific parameters separate shift tables indicating hyper- and hypo- directionality of change will be produced. The laboratory parameters for which CTCAE grade shift outputs will be produced are:

- Haematology: Haemoglobin; Leukocytes; Lymphocytes (count, absolute); Neutrophils (count, absolute); Platelets
- Clinical chemistry: alanine aminotransferase (ALT), aspartate aminotransferase (AST), alkaline phosphatase (ALP), Total Bilirubin, Albumin, Magnesium – low and – high, Sodium – low and – high, Potassium – low and – high, Corrected Calcium – low and – high, Glucose – low and – high, Creatinine, Lipase and Amylase.

Additional summaries will include a shift table for urinalysis (Bilirubin, Blood, Glucose, Ketones, Protein) comparing baseline value to maximum on-treatment value if a sufficient number of urinalysis assessments are recorded.

Haematology, clinical chemistry and urinalysis laboratory data will be listed.

Liver enzyme elevations and Hy's law

A summary will include the number (%) of patients who have:

- Elevated ALT, AST, and Total bilirubin during the study

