 - ALT $\geq 3x$ – $\leq 5x$, $> 5x$ – $\leq 8x$, $> 8x$ – $\leq 10x$, $> 10x$ – $\leq 20x$, and $> 20x$ upper limit of normal (ULN) during the study
 - AST $\geq 3x$ – $\leq 5x$, $> 5x$ – $\leq 8x$, $> 8x$ – $\leq 10x$, $> 10x$ – $\leq 20x$, and $> 20x$ ULN during the study
 - Total bilirubin $\geq 2x$ – $\leq 3x$, $> 3x$ – $\leq 5x$, $> 5x$ ULN during the study
 - ALT or AST $\geq 3x$ – $\leq 5x$, $> 5x$ – $\leq 8x$, $> 8x$ – $\leq 10x$, $> 10x$ – $\leq 20x$, $> 20x$ ULN during the study.
 - ALT or AST $\geq 3x$ ULN and Total bilirubin $\geq 2x$ ULN during the study (Potential Hy's law): The onset date of ALT or AST elevation should be prior to or on the date of Total Bilirubin elevation

This summary will be repeated based on laboratory assessments with a date ≤ 90 days after last dose.

Liver biochemistry test results over time for patients with elevated ALT or AST (i.e. $\geq 3x$ ULN), and elevated Total Bilirubin (i.e. $\geq 2x$ ULN) will be plotted (the onset date of ALT or AST elevation should be prior to or on the date of Total Bilirubin elevation). Individual patient data where ALT or AST (i.e. $\geq 3x$ ULN) plus Total Bilirubin (i.e. $\geq 2x$ ULN) are elevated will be listed also (the onset date of ALT or AST elevation should be prior to or on the date of Total Bilirubin elevation).

Plots of ALT and AST vs. Total Bilirubin by treatment group will also be produced with reference lines at $3 \times ULN$ for ALT, AST, and $2 \times ULN$ for Total Bilirubin. In each plot, Total Bilirubin will be on the vertical axis.

Liver diagnostic investigations, risk factors and lifestyle events as well as liver signs and symptoms will be listed.

Assessment of Thyroid Function Test Results

The following summaries will include the number and percentage of patients who have elevated or low TSH.

- On-treatment elevated TSH $> ULN$
- On-treatment elevated TSH $> ULN$ with TSH $\leq ULN$ at baseline
- On-treatment elevated TSH $> 3 \times ULN$
- On-treatment elevated TSH $> 3 \times ULN$ with TSH $\leq ULN$ at baseline
- On-treatment elevated TSH $> 10 \times ULN$
- On-treatment elevated TSH $> 10 \times ULN$ with TSH $\leq ULN$ at baseline;
- On-treatment low TSH $< LLN$
- On-treatment low TSH $< LLN$ with TSH $\geq LLN$ at baseline

A separate summary will present:

- Number of patients with at least one baseline and post-baseline TSH result
 - o On-treatment elevated TSH $> ULN$ and above baseline
 - o On-treatment decreased TSH $< LLN$ and below baseline

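### The day-90 cut-off for laboratory summaries runs through the middle of the last scheduled laboratory visit (3 months ±1 week after the last dose)

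*SAP*

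**What the plan says.** **Schedule.** Protocol Table 2 is timed by "Time since last dose of IP". It marks haematology, clinical chemistry and TSH at day 30 (±3 days), month 2 and month 3, and the month visits carry ±1 week. Protocol 8.2.1 repeats this for chemistry: "All participants should have further chemistry profiles performed at 30 days", and then at 2 and 3 months, each ±1 week.

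**Analysis.** SAP 4.2.5.2 builds its main tables from "Data obtained up until the 90 days following discontinuation of study treatment (durvalumab/placebo) or until the initiation of the first subsequent anti-cancer therapy", whichever comes first. Some longer-term summaries drop the subsequent-therapy cut but keep the 90-day limit. The section then adds a general rule: "Any data post 90 days after the last dose of the study treatment will not be summarised". The liver-enzyme summary has a second version, "This summary will be repeated based on laboratory assessments with a date" no later than 90 days after the last dose. SAP 3.3 puts the same 90 days into the on-treatment definition, on which the TSH categories and the maximum and minimum values rely.

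**Other relevant rules.**
- SAP 4.1 states: "A year is defined to be 365.25 days and a month is defined to be 30.4375 days".
- SAP 4.1.3 assigns visits by actual date and asks for exhaustive windows, so that any result can potentially be summarised.
- Protocol 9.4.2.1 also defines on treatment, for safety assessments including laboratory data, as ending 90 days after the last dose.

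**The concern.** The visit schedule and the analysis cut-off do not fit together. A participant can have the final safety bloods taken inside the permitted window and still have them left out of every capped table, because the visit fell a few days later than it might have. No other SAP rule brings the result back. Assignment is by actual date, so labelling a day-94 sample as month 3 does not help. The longer-term tables and the repeat liver table have the same limit. For PFS (SAP 3.2.1) and for PROs (SAP 3.2.3.1) the SAP allows for a late visit; for laboratory data it does not.

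The AE tables would not reliably fill the gap. Under Protocol 8.3.7, worsening of a protocol-mandated laboratory value is generally an AE only if it meets seriousness criteria or is the reason for stopping study drug. A non-serious, symptom-free rise in ALT or shift in TSH at month 3 would usually appear in the laboratory summaries or only in a listing. Transaminase increases and thyroid disorders are among the AESIs named in Protocol 8.3.13. At stake is the completeness of the descriptive tables of worst CTCAE grade, liver elevations and TSH shifts for the last part of safety follow-up.

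**Working it through.** The documents give no proportion to reproduce. The check counts how many permitted visit days fall after the cut-off.

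**Inputs**
- Cut-off: day 90 after the last dose (SAP 4.2.5.2).
- Visit tolerance: ±7 days (Protocol Table 2 and 8.2.1), so 7 + 1 + 7 = 15 whole days.
- Length of 3 months, reading A: the performance-status row of Table 2 places post-treatment assessments at 30, 60 and 90 days, so 3 months = day 90.
- Reading B: "a month is defined to be 30.4375 days" (SAP 4.1), so 3 × 30.4375 = 91.3, or day 91 in whole days.
- Reading C: calendar months, 89 to 92 days depending on the last-dose date.

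**Formula.** Window = nominal day − 7 to nominal day + 7. Days after the cut-off = (nominal day + 7) − 90. Share = that number ÷ 15.

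| Reading of 3 months | Window | Days after day 90 | Share | Draw on the nominal day |
|---|---|---|---|---|
| A: 90 days | 83-97 | 97 − 90 = 7 | 7/15 = 47% | kept |
| B: 91 days | 84-98 | 98 − 90 = 8 | 8/15 = 53% | left out |
| C: 89 days (shortest) | 82-96 | 96 − 90 = 6 | 6/15 = 40% | kept |
| C: 92 days (longest) | 85-99 | 99 − 90 = 9 | 9/15 = 60% | left out |

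For reading C, averaged over every last-dose date from 2020 to 2023 (assumed dates, 1,461 of them), the share is 55%. The nominal day falls after day 90 for (313 + 845)/1,461 = 79% of those dates.

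**From days to draws.** These are shares of window days. They equal shares of draws only if attendance is uniform over the window, which is an assumption. If attendance instead peaks at the nominal day, with weights falling linearly to each side, the share after day 90 is 28/64 = 44% on reading A and 36/64 = 56% on reading B.

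**Earlier visits.** The day-30 visit ends at day 33. Month 2 is 2 × 30.4375 = 60.9, or day 61, and its window ends at day 68. Both lie well inside the cut-off, so only the month-3 visit is affected.

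**After the change.** With the cut-off at the end of the window (day 97 on reading A, day 98 on reading B), 0 of 15 in-window days are excluded.

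**Time origin.** Protocol 8.2.1 counts from permanent discontinuation, while the cut-off counts from the last dose. If discontinuation is recorded after the last dose, draws timed from it fall later still relative to day 90.

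**The case against.** The strongest reply is that 90 days is a deliberate, protocol-level limit. Protocol 8.3.2 sets safety follow-up at 90 days, Protocol 9.4.2.1 carries the figure into the on-treatment definition, and SAP 3.3 and 4.2.5.2 apply it, citing attribution to subsequent therapy as the reason for their earlier cut. This stands in part. It explains where the number comes from and means that a longer laboratory window must be recorded as a departure from the protocol. It does not reconcile the number with a scheduled visit that may validly take place after it. The SAP already sets windows by data type, ending ECG and vital-signs data at 30 days (3.3.3 and 3.3.4).

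Second, the practical effect may be small. Main tables already stop at first subsequent therapy, safety summaries are descriptive, and no error-controlled result is touched. All of this stands and limits the weight of the point.

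Three stronger readings are tempting, and the documents do not support them:
- *More than half of the final draws are discarded.* The count is of window days. It drops below half if 3 months means 90 days, and no attendance pattern is given. Nor are the values discarded: haematology, chemistry and thyroid results are listed, and combined transaminase and bilirubin elevations are also listed and plotted individually.
- *Month 3 is the only look at late toxicity.* It is the last of three scheduled post-treatment draws, and the other two are unaffected by the day-90 limit. Late-onset toxicity judged due to study drug also remains reportable as an AE or SAE (Protocol 8.3.2).
- *The treatment comparison is biased.* The rule is the same in both arms, and nothing in the documents shows a differential effect.

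**Conclusion.** The mismatch is real and worth correcting, as a minor point about the completeness of the safety tables. On the two readings that the documents themselves supply, 47% or 53% of the permitted month-3 days lie after the cut-off. Protocol-compliant haematology, chemistry and TSH results can therefore be missing from the summaries while present in the listings. Worst-grade, liver and TSH tables may be incomplete for that visit. Whether they understate anything, and by how much, depends on attendance dates and on how many participants have already started subsequent therapy, and the documents give neither. The conclusion rests on reading the general sentence in SAP 4.2.5.2 as governing all laboratory summaries, which is how it is worded.

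**What to change.** Make one date-rule change in three places: SAP 4.2.5.2, the laboratory use of the on-treatment definition in SAP 3.3, and the repeat liver summary now limited to day 90.

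- End the laboratory window at last dose + 3 months + 1 week, and state how 3 months is counted. With the SAP's month this is day 98. On a calendar count it could reach day 99 (92 + 7), so the rule should name one convention.
- Keep the cut at first subsequent anti-cancer therapy wherever it already applies.
- Record the departure from Protocol 9.4.2.1 in SAP section 6.

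No new data are needed, and neither the visit schedule nor participant management changes. The cost is that the laboratory window would run about a week longer than the AE window. A laboratory value from those days could then be tabulated while an AE starting on the same day is only listed. A footnote on the affected tables would deal with that.

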4.2.5.3 Vital signs

Box plots for absolute values and change from baseline by week may be presented for certain vital signs parameters if warranted after data review.

Vital signs (systolic blood pressure [SBP], diastolic blood pressure [DBP], pulse rate, temperature, respiratory rate and weight) will be summarised over time in terms of absolute values and change from baseline at each scheduled measurement by actual treatment group.

Vital signs data will also be listed.

4.2.5.4 ECGs

ECG evaluations, categorised as detailed in [section 3.3.3](#), will be summarised using a shift table of baseline evaluation to worst evaluation on-treatment if a sufficient number of ECG assessments are recorded.

ECG data and ECG abnormalities will also be listed.

4.2.5.5 Physical examination

Individual physical examination data will not be summarised or listed.

4.2.5.6 Other safety data

Data from positive pregnancy tests will not be summarised. This data will be listed only.

4.2.6 Other exploratory endpoints

4.2.6.1 EuroQol-5-Dimension 5-Level questionnaire (EQ-5D-5L)

The change from baseline in health state utility values and the visual analogue scale (VAS) will be compared between treatment arms at each visit using a MMRM analysis as detailed for the EORTC QLQ-C30 and QLQ-LC13 change from baseline in key symptoms endpoint above, which adjusts for the same factors as the primary analysis and the baseline health state utility value/VAS as appropriate. Adjusted mean differences between treatments and 95% CIs from these analyses will be presented, but, as this analysis is exploratory in nature, p-values will not be calculated.

Descriptive statistics will be reported for the health state utility index score and the VAS index score by visit, as well as the change from baseline of these scores. To support future economic evaluations, additional appropriate analyses may be undertaken, for example, mean health state utility pre- and post-treatment and pre- and post-progression.

A summary of EQ-5D compliance rates will also be presented by visit and overall using the same derivations and analysis methods as the analysis of compliance rates for EORTC QLQ-C30 and QLQ-LC13 above.

EQ-5D-5L utility and VAS scores will be listed.

4.2.6.2 WHO/ECOG performance status

All WHO/ECOG performance status data will be summarised over time for the mITT set, and will also be listed.

4.2.6.3 Health care resource use

An exploratory health economic analysis of hospital episodes including type of contact (hospitalisation, outpatient, or day case), reason, length of stay by ward type (including intensive care unit), procedures, and tests may be undertaken to examine the impact of disease and treatment on health care resource use to primarily support the economic evaluation of durvalumab for the purposes of submissions to payers. To support submissions to payers, additional analyses (including appropriate descriptive statistics such as means, median and ranges) may be undertaken and these will be outlined in a separate Payer Analysis Plan.

Health care resource use data will also be listed.

4.2.7 Pharmacokinetic analysis

Durvalumab concentration data will be listed, and a summary will be provided for all evaluable patients, also by ADA category along with a figure for individual concentration

data. Data collected in this study may be utilised to perform population PK analysis; if this is produced, it will be presented in a separate population PK report.

